# 5.2.2. Analysis of secondary objective outcome measures

*Protective immunity:* Proportions of participants in each category will be presented by trial arm and comparisons between trial arms will be made using chi square test.

*Response waning:* Area under the curve will used for analysis of response waning. Response measurements from weeks 8 and 52 will be used for this analysis.

*Priming versus boosting:* Mean HPV responses will be presented, and a paired t test will be used to compare HPV responses at weeks 8 and 52. In addition, a linear regression model including a time\*trial arm interaction term will be fitted to assess whether the intervention has a differential effect on the response to priming and than to boosting.

*Current malaria infection and intensity:* Proportions of participants with malaria infection will be presented at each timepoint by trial arm and comparisons between trial arms will be made using chi square test. At each timepoint, the means (SD) of malaria infection intensity will be presented by trial arm, and comparisons between trial arms will be made using unpaired t-tests. For both malaria infection status and intensity, Generalised Estimating Equations (GEE) will be used to estimate and compare malaria status and intensity changes between the trial arms.

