# Secondary objectives are:

- a) To determine effects on correlates of protective immunity (where recognised correlates exist).
- b) To determine effects on vaccine response waning.
- c) To determine whether there are differential effects on priming vs boosting immunisations.
- d) To determine effects on current malaria infection prevalence and intensity.

The exploratory objective is to explore immunology among subsets of participants to further characterise effects of preventive treatment of malaria on vaccine responses.

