# 2.7. Timing of outcome assessment

In the following section, week numbers in brackets are based on the schedule in the protocol, with BCG immunisation given at week 0, and YF-17D, Ty21a and first dose of HPV given at week 4 and second dose of HPV and Td given at week 28.

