### Timing of secondary outcomes

*Protective immunity:* Proportions with protective neutralising antibody (YF), i.e. neutralising antibody>1/5; protective IgG levels (TT), i.e. IgG>0.1 IU/ml; seroconversion rates (Ty21a) at four weeks post the corresponding immunisation (week 8).

*Response waning:* Primary outcome measures for all vaccines repeated at week 52 except for Td whose primary outcome responses are measured at week 52.

*Priming versus boosting:* HPV vaccine responses four weeks after the priming dose (week 8) and 24 weeks after the boosting dose (week 52).

Current malaria infection status and intensity at screening (week -8), weeks 0, 4, 8, 52.

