# Analysis population for the secondary outcomes

*Protective immunity:* Analysis population for YF, Ty21a and Td protective immunity will include all enrolled participants who receive the respective vaccine (YF-17D, Ty21a at week 4, Td vaccine at week 28) and have responses to the respective vaccines at 4 weeks post vaccination for YF-17D, Ty21a and 24 weeks post Td vaccination.

*Response waning:* Analysis population will include all enrolled participants who receive any of BCG, YF-17D, Ty21a, HPV and Td vaccines; have corresponding responses to any of these vaccines at weeks 8, 28 (for Td vaccine) and 52 post vaccination.

*Priming versus boosting:* Analysis population will include all enrolled participants who receive a priming dose of HPV vaccine at week 4 and a boosting dose at week 28 and have corresponding responses to the vaccine (at weeks 8 and 52).

Current malaria infection status and intensity: Analysis population will include all enrolled participants who have serum/plasma samples and corresponding results at any of these time points; baseline (week -8), on immunisation days (weeks 0, 4, 8 and 28), and on primary (weeks 8 and 52) and secondary endpoint days (week 52).

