### 5.1.2. Outcomes for secondary objective

- *Protective immunity:* Proportions with protective neutralising antibody (YF), i.e., >1/5; protective IgG levels (TT), i.e., >0.1 IU/mL; seroconversion rates (Ty21a).
- *Response waning:* Primary outcome measures for all vaccines repeated at week 52.
- Priming versus boosting: IgG specific for L1-proteins of HPV-16/18.
- Current malaria infection status and intensity: Infection status (infected and uninfected) and intensity (light, medium and heavy).

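### Response waning is analysed by a two-visit AUC, which measures average level rather than decline; HPV is boosted between the visits, and the SAP contradicts itself on Td

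*SAP*

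**What the plan says.** Secondary objective (b) in SAP 1.2 is "To determine effects on vaccine response waning". The method in 5.2.2 is two sentences: "Area under the curve will used for analysis of response waning. Response measurements from weeks 8 and 52 will be used for this analysis". It names no between-arm test, no effect measure and no list of vaccines. The shell tables in 5.5.3 cover the other three secondary objectives but not waning.

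Three other places bear on which vaccines are included:

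- 2.7, timing of secondary outcomes: "Primary outcome measures for all vaccines repeated at week 52 except for Td whose primary outcome responses are measured at week 52".
- 5.1.2: "Primary outcome measures for all vaccines repeated at week 52", with no exception.
- 3.3, population for secondary outcomes: "all enrolled participants who receive any of BCG, YF-17D, Ty21a, HPV and Td vaccines", who "have corresponding responses to any of these vaccines at weeks 8, 28 (for Td vaccine) and 52 post vaccination".

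The dosing schedule in 2.7 has "second dose of HPV and Td given at week 28".

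**The concern.** Waning is a fall from an early response to a later one. An AUC over many visits describes total exposure, and over only two visits it reduces to the mean of the two values. A participant who starts very high and falls fast can have the same AUC as one who stays moderately high throughout. Used to compare arms, it would report a difference in level as an effect on waning. It would also often miss a real difference in waning.

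Two vaccines raise a separate difficulty. For HPV, a second dose falls between the two samples, so the week 8 to week 52 change mixes decline after priming with the response to the boost. For Td, the sections disagree on whether it belongs in the analysis at all.

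At stake is the interpretation of one pre-specified secondary objective.

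**Working it through.** **The plan's own figure.** The only power figures in the SAP are in Table 1, for the primary analysis population. 341 × 0.60 / 2 = 102 per arm, and 102 × 0.80 = 81.6, i.e. 82. At SD 0.4 and difference 0.20, SE = 0.4 × √(2/82) = 0.0625, z = 0.20/0.0625 = 3.20, and power = Φ(3.20 − 1.96) = 89%, as Table 1 states. All 24 cells reproduce within 1 percentage point. The SAP gives no figure for the waning analysis.

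**Algebra, with no assumptions.** By the trapezoid rule, AUC = (52 − 8) × (y8 + y52)/2 = 44 × (y8 + y52)/2.

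| y8 | y52 | AUC | Change (y52 − y8) |
|---|---|---|---|
| 3 | 1 | 88 | −2 |
| 2 | 2 | 88 | 0 |
| 1 | 3 | 88 | +2 |

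Falling, flat and rising responses share one AUC. Also Cov(y8 + y52, y52 − y8) = Var(y52) − Var(y8), which is zero when the two variances are equal. AUC is then uncorrelated with decline.

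**Size.** Inputs: 82 per arm (Table 1), SD 0.4 log10 at both visits (within Table 1's range), two-sided 5% (SAP 3.1), and within-person correlation ρ = 0.5 (assumption; the SAP gives none).

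- Mean level (AUC/44): SD = 0.4 × √((1 + 0.5)/2) = 0.346; SE = 0.346 × √(2/82) = 0.054.
- Change: SD = 0.4 × √(2 × (1 − 0.5)) = 0.4; SE = 0.0625.

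| Arm difference at weeks 8 / 52 (log10) | Difference in mean level | Difference in change | AUC significant | Change significant |
|---|---|---|---|---|
| +0.2 / +0.2 (no waning difference) | 0.2 | 0 | about 96% | 5% |
| 0 / 0.2 | 0.1 | 0.2 | about 46% | about 89% |
| +0.1 / −0.1 (crossing) | 0 | 0.2 | 5% | about 89% |

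Direction can mislead too. If DP is 0.2 higher at week 8 and equal at week 52, DP wanes faster. The mean-level difference is again 0.1, so the AUC is significant in about 46% of trials, almost always in favour of DP.

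**Range.** At SD 0.5 with ρ = 0.3 / 0.5 / 0.7:

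| Case | AUC | Change |
|---|---|---|
| +0.2 / +0.2 | 89% / 84% / 79% | 5% |
| 0 / 0.2 | 36% / 32% / 28% | 58% / 73% / 91% |
| +0.1 / −0.1 | 5% | 58% / 73% / 91% |

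**Vaccines, section by section.**

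- BCG, YF-17D and Ty21a: weeks 8 and 52 are both planned, and 2.7 lists no further dose between them.
- HPV: the second dose is at week 28. The same section describes week 52 as 24 weeks after the boost, and 5.2.2 uses the same two samples for priming versus boosting. No section excepts HPV from waning.
- Td: 2.7 makes an exception ("except for Td whose primary outcome responses are measured at week 52"), 5.1.2 makes none, and 3.3 includes it with a week-28 value. Week 28 is the day of the dose and week 8 is 28 − 8 = 20 weeks before it. The only listed post-dose sample is week 52, so no post-dose decline can be estimated. Section 3.3 also labels weeks 8, 28 and 52 as counted from vaccination, whereas 2.7 uses them as study weeks.

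**The case against.** Several counter-arguments have weight.

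- A reader might infer that the waning objective cannot be answered. The documents do not support that: for BCG, YF-17D and Ty21a both samples are planned with no dose between them. The summary is at fault and the data are adequate.
- A reader might infer that AUC is blind to waning. It is blind only when the arms cross symmetrically. If they are equal at week 8, half of a week-52 difference enters the mean level, at lower power.
- A reader might take a Td waning analysis as settled. It is not: 2.7 excepts Td, 5.2.2 lists no vaccines, and the week-28 value in 3.3 has no place in a method limited to weeks 8 and 52. The SAP contradicts itself here.
- The 82 per arm describes the malaria-infected population, while 3.3 also plans an analysis of all randomised participants. With 341 / 2 × 0.80 ≈ 136 per arm, AUC power in the 0 / 0.2 case rises to about 66%. More participants do not make the AUC specific to waning: false attribution in the parallel case becomes more frequent.
- Week-8 differences are reported as primary results, so an AUC would not be read alone, and the HPV contrast is covered by the time-by-arm term in 5.2.2. Both soften the harm. Neither supplies a waning estimate for BCG, YF-17D or Ty21a.
- The authors may have meant an AUC measured relative to the week-8 value. That would be 44 × (y52 − y8)/2 = 22 × change and would serve, but the SAP does not say so.

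**Conclusion.** The point stands. As written, 5.2.2 tests average level under the name of waning, and nothing elsewhere in the SAP repairs this. That part is algebra and depends on no assumed effect size. The percentages rest on equal SDs at the two visits, a normal approximation and an assumed correlation, so they are illustrations. The crossing pattern is the extreme case; the fairer measure of lost power is the equal-at-week-8 case, with about 46% against 89% at SD 0.4, or 28–36% against 58–91% at SD 0.5.

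HPV should not be in a week 8 to week 52 waning analysis, and the sections on Td must be reconciled. The issue is confined to one secondary objective. It should be corrected before analysis but does not threaten the primary conclusions.

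**What to change.** 1. In 5.2.2, replace the AUC with the between-arm difference in log10 change (week 52 minus week 8), with a 95% CI, for BCG, YF-17D and Ty21a. The arm-by-time term that the section already uses for HPV is an alternative, fitted so that each participant's two values are treated as paired. The two agree for complete pairs but can differ when one visit is missing, so state which is used. Week 52 adjusted for week 8 is another defensible choice.
2. Report the week-52 between-arm difference beside it. If the AUC is kept, label it a descriptive summary of overall level.
3. Remove HPV and Td from the waning analysis. HPV weeks 8 and 52 stay under priming versus boosting, and Td week 52 stays a primary outcome.
4. Make 2.7, 3.3, 5.1.2 and 5.2.2 agree on vaccines and time points, call the weeks study weeks in 3.3, and add a shell table for waning.

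The cost is SAP wording only, with no new samples or assays. HPV and Td would no longer be reported under waning.

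### The HPV priming-versus-boosting interaction is assigned to a linear regression with no provision for two correlated measurements per participant, so as written its standard error is likely too large

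*SAP*

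**What the plan says.** Section 1.2 lists, as secondary objective (c), whether effects differ between priming and boosting immunisations. Section 5.2.2 gives two analyses for it, the first within person and the second comparing the arms: "a paired t test will be used to compare HPV responses at weeks 8 and 52. In addition, a linear regression model including a" time-by-arm term, where the "trial arm interaction term will be fitted to assess whether the intervention has a differential effect on the response to priming" and to boosting.

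The population for this outcome (section 3.3, secondary outcomes) is limited to participants who had both HPV doses and who "have corresponding responses to the vaccine (at weeks 8 and 52"). Everyone analysed therefore supplies exactly two values.

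For the other repeated outcome, the same section names a method for correlated data: "For both malaria infection status and intensity, Generalised Estimating Equations (GEE) will be used".

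Nothing else in the SAP adds a correlation structure to the HPV model. The paragraph on checking assumptions covers normality and equal variances, not independence. Table 5 shows only paired t test P values, so no table shell clarifies the interaction model.

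**The concern.** The time-by-arm interaction is the difference between arms in the mean within-person change from week 8 to week 52. A person's general level of response cancels from that change, which is what makes it precise when the two values are positively correlated. A linear regression on the stacked values, with its usual standard errors, treats the two rows of one person as if they came from two people. It therefore puts back the between-person variation that the contrast removes.

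The paired t test, as laid out in Table 5, compares weeks within each arm. The interaction is thus the only stated analysis of objective (c) that uses the randomised comparison. If its standard error is too large, the confidence interval is too wide and the P value too high, and a null result could be read as firmer evidence against a differential effect than it is. The achieved sample is 341 against a target of 640 (section 2.2), so there is little precision to spare.

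**Working it through.** **Inputs from the SAP.** Two-sided 5% tests (section 3.1); 1:1 allocation (section 2.1); 82 per arm after 20% loss and log10 SDs of 0.3 to 0.6 (section 2.2, Table 1); two HPV values per participant (section 3.3).

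**Assumed, because the SAP does not give it.** The correlation rho between a participant's week 8 and week 52 HPV responses; range 0.3 to 0.7. Equal SDs at the two weeks at first, then relaxed.

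**Step 1: reproduce the plan's own figure.** The SAP states no power for the interaction, so Table 1 is the only figure to check. 341 × 0.60 / 2 = 102.3, and 102.3 × 0.80 = 81.8, which gives 102 and 82 per arm. For SD 0.4 and difference 0.20, SE = 0.4 × sqrt(2/82) = 0.0625, and power = Φ(0.20/0.0625 − 1.96) = 89%, as stated. All 24 cells of Table 1 reproduce to within one percentage point.

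**Step 2: standard error of the interaction, n per arm, equal SDs.**
- Regression that treats rows as independent: sqrt(4 × SD² / n)
- Respecting the pairing: sqrt(4 × SD² × (1 − rho) / n)
- Ratio: 1 / sqrt(1 − rho), whatever n and SD are

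With SD 0.4 and n = 82, the first is sqrt(4 × 0.16 / 82) = 0.088 for every rho.

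**Step 3: true type I error and power.** The true type I error of a nominal 5% test is 2 × [1 − Φ(1.96 × ratio)]. For a fixed difference in differences of 0.20 log10, power is Φ((0.20 − 1.96 × SE_independent) / SE_paired) under the regression, and Φ(0.20 / SE_paired − 1.96) when pairing is respected.

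| Assumed rho | SE, independent | SE, paired | Ratio | True type I error | Power, independent | Power, paired |
|---|---|---|---|---|---|---|
| 0.3 | 0.088 | 0.074 | 1.20 | 1.9% | 64% | 77% |
| 0.5 | 0.088 | 0.062 | 1.41 | 0.6% | 67% | 89% |
| 0.7 | 0.088 | 0.048 | 1.83 | 0.03% | 71% | 98.5% |

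**Step 4: simulation check** (4,000 trials per rho, SD 0.4, 82 per arm). At rho 0.5 the estimate's empirical SD was 0.064, the mean regression SE 0.088 and the mean paired SE 0.062. Under the null, 0.55% of regression tests and 5.4% of paired tests rejected.

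**Step 5: unequal SDs.** The ratio becomes sqrt((s1² + s2²) / (s1² + s2² − 2 × rho × s1 × s2)). With SDs 0.3 and 0.6 it is 1.15, 1.29 and 1.51 at rho 0.3, 0.5 and 0.7.

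**Step 6: larger population.** Table 1's 82 per arm refers to participants infected at baseline. If all enrolled participants were analysed with the same 20% loss (an assumption), n = 341 × 0.80 / 2 ≈ 136 per arm. Power for the same effect is then 87%, 91% and 96% under the regression, against 94%, 98% and over 99% with pairing, at rho 0.3, 0.5 and 0.7.

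**The case against.** **The SAP does not say ordinary least squares.** It says linear regression and is silent on within-participant correlation. A linear regression with standard errors clustered by participant would still fit the wording, and authors who name a paired t test and GEE in the same section clearly know that the data are repeated. This stands in part. A reader might infer that the plan has chosen the wrong standard error; the text supports only that it names a model whose usual standard error is wrong here and does not name the correction. Every consequence above is conditional on that usual standard error being used.

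**A reader might also infer that a real difference will probably be missed.** The documents do not support that. If the assumed effect is reset at each rho so that the paired analysis always has 80% power, power under the regression appears to fall steeply as rho rises, but only because the effect shrinks. With the effect held at 0.20 log10 and SD 0.4, power under the regression is 64% to 71%. The true statement is that a real difference is more likely to be missed than it need be.

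**The size rests on unknowns.** This stands. Rho is not given, and at rho = 0 there is no inflation. At a negative rho the error would reverse (ratio 0.91 at −0.2), though that is implausible for two antibody levels in one person. The 82 per arm is illustrative, and the absolute loss of power is smaller if all enrolled participants are analysed.

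**The consequence is limited.** This also stands. It is a secondary outcome, the error is conservative, and the primary analyses are not touched. Because everyone analysed has both values, the point estimate is the same under either approach.

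**Conclusion.** The point holds as a defect in a secondary analysis that should be corrected. Followed as written with standard errors that assume independence, the regression gives an interaction standard error that is 20% to 83% too large for rho 0.3 to 0.7 with equal SDs, or about 15% to 51% too large with SDs of 0.3 and 0.6. The direction is secure for any positive rho and does not depend on sample size; the size is an assumed range.

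It is more than missing detail, because the method as named performs worse than alternatives that the same section already uses. It does not produce false positives or bias the estimate. It costs precision in the one randomised comparison for objective (c): 13 to 27 percentage points of power in the 82-per-arm illustration, and about 4 to 7 points with 136 per arm.

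**What to change.** In section 5.2.2, under priming versus boosting, replace the linear regression sentence by one of these:

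- Compare between arms each participant's change in HPV response (week 52 minus week 8), on the scale chosen under the SAP's assumption checks, and report the difference in mean change with its 95% confidence interval and P value.
- Keep the time-by-arm term, but fit it with a participant random intercept, or by GEE or linear regression with standard errors clustered by participant.

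The first is the simplest: the population already requires both measurements, so it is an unpaired comparison of one number per person. A line for the interaction estimate in Table 5 would show where the result is reported. The cost is one SAP sentence and a line of code, with no new data or visits. The change should be made before unblinding.

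### The HPV time-by-arm interaction compares the DP effect 4 weeks after dose 1 with that 24 weeks after dose 2, so it mixes any priming/boosting difference with any DP effect on persistence

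*SAP*

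**What the plan says.** Secondary objective (c) in SAP 1.2 is "To determine whether there are differential effects on priming vs boosting immunisations". Objective (b), just before it, concerns effects on the waning of vaccine responses.

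On timing, SAP 2.7 has the "first dose of HPV given at week 4 and second dose of HPV and Td given at week 28". The same section defines the priming-versus-boosting outcome as "HPV vaccine responses four weeks after the priming dose (week 8) and 24 weeks after the boosting dose (week 52"). The analysis population in SAP 3.3 consists of those who receive both doses and "have corresponding responses to the vaccine (at weeks 8 and 52").

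On analysis, SAP 5.2.2 says "a paired t test will be used to compare HPV responses at weeks 8 and 52". It then adds a linear regression with a time-by-arm interaction, "fitted to assess whether the intervention has a differential effect on the response to priming and than to boosting". This interaction is the only between-arm test specified for objective (c). No sentence limits its interpretation on account of the unequal intervals.

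The Table 5 shell (SAP 5.5.3) heads its second column as four weeks after the boosting dose, which would be week 32. Sections 2.7, 3.3 and 5.2.2 provide no HPV measurement at that week.

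**The concern.** The two measurements differ in two respects: which dose came last, and how long ago it was given. A model with two time points cannot separate these. If DP changes how fast antibody declines, the interaction moves away from zero even when DP acts in the same way on the response to each dose. A persistence effect in the opposite direction to a real priming/boosting difference can also shrink or hide that difference.

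Waning is not a remote possibility that the SAP could leave aside. It is an objective of the trial, and its analysis in 5.2.2 uses the same two weeks, 8 and 52. The same pair of HPV measurements is thus read as waning under (b) and as priming versus boosting under (c).

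At stake is the sentence the trial will write about objective (c). A significant term would be reported as DP affecting priming and boosting differently, and a null term as DP affecting them alike. Neither follows from the contrast alone.

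**Working it through.** **Intervals (SAP 2.7).** Dose 1 is at week 4 and its sample at week 8: 8 − 4 = 4 weeks. Dose 2 is at week 28 and its sample at week 52: 52 − 28 = 24 weeks. Time since the last dose differs by 20 weeks. A post-boost sample matched to the priming sample would fall at 28 + 4 = week 32.

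**What the interaction estimates.** Write E(w) for the DP-minus-placebo difference in mean log10 HPV IgG at week w. Then

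interaction = E(52) − E(8) = [E(32) − E(8)] + [E(52) − E(32)].

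The first bracket is the priming/boosting difference at equal time since dose. The second is the DP effect on the change from week 32 to week 52. Only the sum is observed. It equals the first bracket only when the second is zero.

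**The SAP's own figures.** Table 1 gives power for the primary comparison, not for this one, but it supplies a sample size and a range of SDs. Sample size: 341 × 0.6 / 2 ≈ 102 per arm, and 102 × 0.8 ≈ 82. A two-sample t test (non-central t, 162 df, two-sided 5%) gives 56.4% at SD 0.3 and difference 0.10, 60.6% at 0.4 and 0.14, and 72.1% at 0.5 and 0.20. The table prints 56%, 61% and 72%. All 24 cells reproduce, and nothing in this point disturbs them.

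**Illustration.** From Table 1: n = 82 per arm and SD 0.3 to 0.6 log10. Assumed, not in the SAP: within-person correlation r between weeks 8 and 52 of 0.3 to 0.7; equal SD at both weeks; an analysis that respects the pairing; and DP acting identically on both doses (true priming/boosting difference zero), with its effect falling by x between 4 and 24 weeks.

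SE = SD × √(2(1 − r)) × √(2/n)

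- Central case, SD 0.4, r 0.5: 0.4 × √1 × √(2/82) = 0.0625.
- Smallest SE, SD 0.3, r 0.7: 0.3 × √0.6 × √(2/82) = 0.0363.
- Largest SE, SD 0.6, r 0.3: 0.6 × √1.4 × √(2/82) = 0.1109.

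The chance of a significant interaction (non-central t with parameter x/SE, 162 df) is:

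| Fall x (log10) | SD 0.6, r 0.3 | SD 0.4, r 0.5 | SD 0.3, r 0.7 |
|---|---|---|---|
| 0.07 (effect 0.14 at 4 weeks, 0.07 at 24) | 10% | 20% | 48% |
| 0.14 (effect gone by 24 weeks) | 24% | 61% | 97% |

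The nominal rate is 5%. If all randomised participants are analysed, 341 × 0.8 / 2 ≈ 136 per arm, and the central column becomes 30% and 82%. A smaller fall of 0.035 at SD 0.4, r 0.5 and 82 per arm gives 9%.

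**The other direction.** Suppose DP's effect at 4 weeks is 0.14 after dose 1 and 0.28 after dose 2, and halves by 24 weeks. The planned contrast is 0.28/2 − 0.14 = 0, so a true doubling is invisible to it. These values were chosen to cancel exactly. They show that masking can occur, not how likely it is.

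**The case against.** The best defence is that the SAP is open about what it compares: 2.7 states both intervals, so a careful reader can see that they differ. If DP does not alter decay, the interaction is an unbiased test of a priming/boosting difference. Listing waning as an objective poses a question and does not predict an effect of any size. The rejection rates depend on assumed falls of 0.07 and 0.14, and they shrink as the fall shrinks or the SD grows. The outcome is secondary.

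All of that stands, and it limits the point. It does not remove it, because 5.2.2 gives the term a meaning that needs the no-decay-effect assumption and does not state the assumption. Giving the intervals in 2.7 does not warn against the interpretation in 5.2.2, and the Table 5 heading suggests equal intervals that the rest of the SAP does not have.

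A reader might also infer that the SAP already holds a matched contrast: week 28 is 24 weeks after dose 1 (28 − 4), and week 52 is 24 weeks after dose 2. The document does not securely support this. SAP 3.3 mentions "serum/plasma samples and corresponding results at any of these time points; baseline (week -8), on immunisation days (weeks 0, 4, 8 and 28") for malaria status, but 2.7 and the Table 6 footnote give weeks -8, 0, 4, 8 and 52 without 28. The same list calls week 8 an immunisation day, although 2.7 schedules no vaccine then. The waning population in 3.3 refers to "responses to any of these vaccines at weeks 8, 28 (for Td vaccine) and 52 post vaccination", yet 2.7 exempts Td from the week-52 repeat and 5.2.2 uses only weeks 8 and 52. Nothing says that week-28 serum was drawn before dose 2 or kept for HPV assays. Even a matched contrast would address 24-week persistence rather than the 4-week response, and week 52 reflects both doses.

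**Conclusion.** The stated interpretation of the interaction is wrong as written. The term estimates the DP effect 24 weeks after dose 2 minus the DP effect 4 weeks after dose 1. It mixes any priming/boosting difference with any DP effect on persistence, and it tests objective (c) only if DP leaves antibody decay unchanged. The within-arm paired t test has the same mismatch in time since dose.

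Under the assumptions listed, a persistence effect alone makes the term significant in about 10% to 48% of trials for a fall of 0.07 log10 and about 24% to 97% for 0.14. These figures show sensitivity. They do not predict what DP does.

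A reader might infer that the analysis cannot answer objective (c) at all, or that the term measures only persistence. Neither follows: the bias is zero if decay is unaffected, and a real priming/boosting difference does contribute to the term. The wording should be corrected before the analysis. The primary HPV comparison at week 8 is not touched.

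**What to change.** In SAP 5.2.2, restate the interaction as the difference between the DP effect 4 weeks after dose 1 and the DP effect 24 weeks after dose 2. Add that a non-zero or null term is not by itself evidence for or against a priming/boosting difference, because time since dose differs. Attach the same caveat to the within-arm paired t test. Make the second column heading of Table 5 agree with sections 2.7, 3.3 and 5.2.2.

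This costs only wording. The price is a narrower conclusion for objective (c).

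Optional, and only if stored week-28 serum drawn before dose 2 is confirmed to exist: add a sensitivity contrast of HPV-16/18 IgG at week 28 versus week 52 by arm, which equalises time since dose at 24 weeks. This needs additional HPV assays. Its report should say that it targets persistence at 24 weeks and that week 52 reflects both doses. Week 8 stays as the primary HPV outcome.
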